5.6 Investigational Drug Handling and Disposal

All study drug samples will be accounted for on drug inventory records (including records of study drug sent to the Investigator and records generated at the investigational site). The Sponsor and/or its designate will review inventory forms during the study and at the conclusion of the study. The Investigator will sign the drug inventory record after resolving any questions resulting from the Sponsor and/or its designee's review. The Investigator must retain a copy of all drug inventory records.

All remaining used and unused study drug must be retained until final instructions are given by the Sponsor.

Tris Pharma will provide detailed drug return instructions to the study site. All post-treatment handling and disposal of study drug will be in accordance with GCP and cGMP guidelines and federal and local regulations.

Confidential Page 37 of 67

6 SUBJECT COMPLIANCE

6.1 Concomitant Medication and/or Therapy

Concomitant medications information will be collected beginning at Screening and will continue during all study visits or Early Termination (EOT) visit, if applicable.

6.2 Prohibited Concomitant Medications

Psychotropic medications are not allowed during the study except for stimulants (other than study drug), which must be discontinued within 7 days of Baseline. No anticonvulsant, antidepressant, or antipsychotic medications are permitted during the study. Melatonin is permitted. Prohibited concomitant medications may be resumed 1 day after Study Visit 4 (or EOT).

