3.4 Exclusion Criteria

The presence of any of the following exclusion criteria precludes a subject from study enrollment:

- 1. Current or lifetime history of bipolar disorder or any psychotic disorder as established by Mini International Neuropsychiatric Interview (M.I.N.I.) 7.0.2.
- 2. Current history of major depression generalized anxiety disorder, obsessive-compulsive disorder, panic disorder, or post-traumatic stress disorder as established by the M.I.N.I. 7.0.2.
- 3. Known history of chronic medical illnesses including untreated thyroid disease, peripheral vasculopathy, known structural cardiac disorders, serious cardiac conditions, serious arrhythmias, cardiomyopathy, and known family history of sudden death.
- 4. History of uncontrolled hypertension or a resting systolic blood pressure >140 mmHg or diastolic blood pressure >90 mmHg. Subjects with well-controlled hypertension on a stable dose for at least 3 months of anti-hypertensives will be allowed to participate.
- 5. Have clinically significant findings in vital signs measurements at Screening including:
 - Systolic blood pressure >140 mmHg or diastolic blood pressure >90 mmHg
 - Heart rate >100 bpm
- 6. Known history or presence of significant renal or hepatic disease, as indicated by clinical laboratory assessment (clinically significant liver function tests, blood urea nitrogen, or creatinine levels)
- 7. Clinically significant abnormal electrocardiogram or cardiac findings on physical examination (including the presence of a pathologic murmur).
- 8. Use of the following medications within 14 days of Baseline Visit:
 - Atomoxetine
 - Monoamine oxidase inhibitors (e.g., selegiline, isocarboxazid, phenelzine, tranylcypromine)
 - Tricyclic antidepressants (e.g., desipramine, protriptyline).
- 9. Use of the following medications within 3 days of Baseline Visit:

Confidential Page 24 of 67

- Gastrointestinal acidifying agents (e.g., guanethidine, reserpine, glutamic acid hydrochloride [HCl], ascorbic acid)
- Urinary acidifying agents (e.g., ammonium chloride, sodium acid phosphate, methenamine salts).
- 10. Use of fluoxetine within 30 days of Baseline Visit.
- 11. Use of stimulant medications within 1 week of Baseline Visit.
- 12. Planned use of prohibited drugs or agents from the Screening visit through the end of the study.
- 13. Participation in a clinical study in which an investigational drug was administered within 30 days prior to Screening.

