4.2.10.4 Visit 4 (Day 28) Abbreviated administration of serial PERMPs

The following assessments will be performed at Visit 4:

- Blood pressure and pulse (average of triplicate measurements) at pre-dose and ~3 hours post-dose
- Body weight
- Abbreviated administration of serial PERMPS at pre-dose, 0.5, 1, 2 and 4 hours post-dose. Pre-dose PERMP will be administered approximately 30 minutes prior to dosing, followed by on-site administration of AMPH ER TAB 20 mg or matching placebo by the clinic staff.

Confidential Page 32 of 67

- AISRS
- CGI-S
- "Since Last Visit" C-SSRS
- Questionnaire for Sleep, Appetite, Mood, and Psychotic Adverse Events
- AE assessment
- Concomitant medications assessment
- DB AMPH ER TAB 20 mg or matching placebo dispensing, accountability, and subject training regarding investigational drug.

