6.2.1 Prohibited Concomitant Medications

Any stimulant (e.g., methylphenidate, dexmethylphenidate, amphetamine, and dextroamphetamine) should be discontinued 7 days prior to Baseline. The following medications are prohibited during the study:

Selective serotonin reuptake inhibitors (SSRIs) (e.g., paroxetine)

Serotonin and norepinephrine reuptake inhibitors (SNRIs) (e.g., desvenlafaxine, duloxetine, venlafaxine – with the exception of fluoxetine which is restricted for 30 days prior to Baseline) MAOIs

Mood stabilizers (e.g., lithium, valproate, quetiapine)

Antipsychotics (e.g., risperidone, olanzapine)

Anticonvulsants (e.g., phenobarbital, phenytoin, primidone)

Sedative hypnotics, except melatonin

Anticoagulants

Halogenated anesthetics

Tricyclic antidepressants

Atomoxetine

Guanfacine

Clonidine

CYP2D6 inhibitors (e.g., paroxetine and fluoxetine, quinidine, ritonavir)

Fentanyl, tramadol, tryptophan, buspirone, St. John's Wort

Gastrointestinal acidifying agents (e.g., guanethidine, reserpine, glutamic acid HCl, ascorbic acid)

Urinary acidifying agents (e.g., ammonium chloride, sodium acid phosphate, methenamine salts

Decongestants (e.g. oxymetazoline, phenylephrine, pseudoephedrine)

Sedating antihistamines (e.g. alimemazine, chlorphenamine, clemastine, cyproheptadine, hydroxyzine, promethazine)

Acetaminophen is permitted for control of fever or pain if needed. Short courses of prescription and non-prescription medications needed for treatment of acute illnesses such as the common cold, viral illnesses, and ear infections are permitted as long as these do not contain medications listed above. Ongoing antihypertensive treatment will be assessed by the Investigator and the Sponsor.

Confidential Page 38 of 67

Alcohol consumption will be restricted form Baseline to 24 hours after Visit 5.

All concomitant medications must be recorded on the Concomitant Medication CRF.

The Investigator should contact the Medical Monitor for a written Note to File or Memo to File for evidence that the Sponsor is aware of a chronic or acute medication and a judgment on whether the subject may continue in the study.

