7 RANDOMIZATION AND BLINDING PROCEDURES

Enrollment will occur after all Screening procedures have been performed and eligibility for the study is confirmed at Baseline. After Baseline, subjects will enter a 4-week randomized, DB, placebo-controlled phase. Subjects will be randomized at Baseline to take DB AMPH ER TAB (or matching placebo) orally once daily.

All study drug product samples will be supplied in identical containers and will be similar in physical characteristics (color, smell, flavor, and appearance), thereby enabling DB conditions.

Unblinding should occur only when knowing the treatment assignment has a bearing on the medical treatment or evaluation of a subject. Whenever possible, the need to unblind should be discussed with the Sponsor prior to unblinding. For emergency unblinding, study personnel will use the IWRS unblinding module.

Table 6 Sponsor's Contact Information for Unblinding Procedures

Contact	Phone number	Fax number
Tris Pharma, Inc		
[name] Director, Regulatory Affairs	Direct # [contact]	NA
[contact]		

A subsequent written report, including all pertinent details, must be submitted to the Sponsor within 24 hours of the unblinding. Whenever possible, the blind of the subject should be maintained.

If Investigator or site personnel or subject unblinded, the subject must be withdrawn from the study, and procedures accompanying withdrawal are to be performed.

Confidential Page 40 of 67

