8.2.2 Serious Adverse Events That Occur After Study Completion

If the Investigator becomes aware of an SAE or death that occurs in a subject within 30 days after Visit 4and that Investigator considers the event to be related to the study medication, the Investigator is obligated to report the SAE to the Sponsor.

Confidential Page 42 of 67

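### Section 6.2 lets prohibited medications restart 1 day after Visit 4, nominally 6 days before the primary endpoint is measured at Visit 5

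*Combined protocol and SAP*

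**What the plan says.** Section 6.2 closes with the only restart rule in the protocol: "Prohibited concomitant medications may be resumed 1 day after Study Visit 4 (or EOT"). Section 6.1 uses EOT for the early termination visit, so subjects who complete the study fall under the Visit 4 part of the rule.

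The rest of the protocol treats Visit 5 as the end:

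- Section 6.2.1 introduces its list with "The following medications are prohibited during the study". The list includes atomoxetine, guanfacine, clonidine, MAOIs and tricyclics.
- Exclusion Criterion 12 (Section 3.4) bars "Planned use of prohibited drugs or agents from the Screening visit through the end of the study".
- Section 6.2.1 also says "Alcohol consumption will be restricted form Baseline to 24 hours after Visit 5".
- Section 4.2.10.4 (Visit 4, Day 28) includes "DB AMPH ER TAB 20 mg or matching placebo dispensing, accountability, and subject training regarding investigational drug", so blinded treatment continues after that visit. Section 4.2.10.5 (Visit 5, Day 35) has the 20 mg dose given on site, followed by the full serial PERMP.

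On stimulants, Section 6.2 disallows psychotropic drugs "except for stimulants (other than study drug), which must be discontinued within 7 days of Baseline". Section 6.2.1 repeats the instruction to stop 7 days before Baseline, but does not include stimulants in the itemised list.

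**The concern.** The restart rule removes the medication restriction during the last week of blinded treatment, just before the only visit that yields the primary endpoint and the gated time-point tests. A site that follows it could allow a subject to restart atomoxetine, guanfacine or clonidine before Visit 5. Stimulants appear under the same heading of prohibited drugs, so the natural reading is that the permission covers them too. That reading is an inference, and the text should settle it.

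Nothing later in the plan undoes the effect. The estimand in Section 3.2.1 counts scores whatever concomitant medication was taken. The mITT population in Section 9.2 requires only one PERMP-T score at Visit 5. The sensitivity analysis in Section 9.3.5.1 addresses missing data only. Concomitant medications are recorded at Visit 5, so reported use would be seen. The Visit 5 drug screen (Table 5) does not include amphetamines, so it would not reveal unreported amphetamine use.

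Use in the placebo arm would dilute the treatment difference; use in the active arm could inflate it. There is also a safety side. MAOIs are on the prohibited list, and Exclusion Criterion 8 requires 14 days without them before Baseline, yet the rule would let them return while subjects may be taking amphetamine 20 mg.

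**Working it through.** **Dates.** Visit 4 is Day 28 (Section 4.2.10.4) and Visit 5 is Day 35 (Section 4.2.10.5). Earliest restart = 28 + 1 = Day 29. Time from restart to the endpoint = 35 − 29 = 6 days.

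With the ±3-day windows of Section 9.3.8 applied to both visits:

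- shortest: Visit 4 on Day 31, Visit 5 on Day 32; 32 − (31 + 1) = 0 days
- longest: Visit 4 on Day 25, Visit 5 on Day 38; 38 − (25 + 1) = 12 days

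If the sentence named Visit 5, the earliest restart would be Day 36, after the endpoint.

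**Is it a leftover?** Section 7 says "After Baseline, subjects will enter a 4-week randomized, DB, placebo-controlled phase", whereas Section 3.1 describes a 5-week double-blind phase. Section 8.2.2 sets the post-study SAE rule for an event "that occurs in a subject within 30 days after Visit 4and that Investigator considers" to be drug-related. Section 8.3 ends the AE reporting period at Visit 4, although Section 4.2.10.5 schedules an AE assessment at Visit 5. All three treat Visit 4 or week 4 as the end of the study, which supports a stale visit number as the cause.

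**Reference power.** Section 9.1 gives an effect size of 0.80, about 92 completers and at least 93% power. At 0.80 with an assumed 46 per arm, two-sided 0.05, noncentral-t power is 96.7%, consistent with that statement. The same section's components give 18/21.75 = 0.828 and power of 97.5%. The scenarios below start from those components.

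**Placebo-arm use.** Suppose a fraction f of placebo subjects resume and gain a fraction b of the 18-point benefit:

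difference = 18 × (1 − f × b)

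Power is noncentral t with noncentrality (difference/21.75) × √(46/2) and 90 degrees of freedom. For example, f = 0.20 and b = 0.5 give 18 × 0.90 = 16.2, noncentrality 3.57 and power 94.2%.

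| f | b = 0.5: difference | b = 0.5: power | b = 1.0: difference | b = 1.0: power |
|---|---|---|---|---|
| 0 | 18.0 | 97.5% | 18.0 | 97.5% |
| 0.10 | 17.1 | 96.2% | 16.2 | 94.2% |
| 0.20 | 16.2 | 94.2% | 14.4 | 88.1% |
| 0.30 | 15.3 | 91.6% | 12.6 | 78.5% |

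b = 1.0 is an upper bound. The SD is held at 21.75. Part of any gain may also be adjusted away, because the pre-dose PERMP-T score at Visit 5 is a covariate and could itself be raised by resumed medication.

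**Active-arm use.** If a fraction g of active subjects gain an extra 9 points, the difference is 18 + 9g: 18.9 for g = 0.10 and 19.8 for g = 0.20.

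The values of f, b, g and the 9 points are assumptions; the documents give none of them.

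**The case against.** The strongest reply is that this is a conflicting instruction rather than a clear permission. Sections 6.2 and 6.2.1 prohibit these drugs for the whole study, and Section 4.2.10 lists Visit 5 as part of it. Exclusion Criterion 12 should keep out anyone who plans to resume early. Section 6.2.1 also has the investigator contact the Medical Monitor about a chronic or acute medication, for a decision on whether the subject continues. These points stand, and they make use before Visit 5 less likely. They do not remove the permission: a specific restart date can reasonably be read as overriding a general ban.

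No text expressly permits a stimulant restart, and resuming applies only to drugs a subject took before. That is right, and it is why the stimulant rule needs its own sentence.

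The power figures rest on assumed rates. For placebo use of 10% or 20% at half benefit, or 10% at full benefit, power stays at or above 94.2%, within the planned 93%. Similar use and gain in both arms would largely cancel. This also stands: the case for the change does not rest on a predicted loss of power.

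Finally, the estimand includes scores after concomitant use, so such scores are formally on target. That is true of the wording, but it means the analysis would absorb the contamination rather than correct it.

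**Conclusion.** The concern holds and the sentence must be corrected. As written, Section 6.2 permits prohibited medications from Day 29, nominally 6 days before the primary endpoint (0 to 12 days with the windows), during blinded dosing and in conflict with Exclusion Criterion 12 and Section 6.2.1. The dates and the contradiction come directly from the text, and confidence in them is high. That the visit number is stale is a well-supported inference. That the rule extends to stimulants is the natural reading but not certain.

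The consequence cannot be sized from the documents. Under the assumed rates of placebo resumption it ranges from slight (10% at half benefit) to serious (30% at full benefit). Active-arm use would bias the difference upwards. The severity rests on a wrong operational instruction ahead of the only endpoint visit, and on the fact that affected Visit 5 scores could not be collected again.

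**What to change.** In Section 6.2, change the visit number in the last sentence from 4 to 5, so that prohibited medications may restart 1 day after Visit 5, or after early termination. In Section 6.2.1, add one sentence stating that stimulants other than study drug are prohibited from 7 days before Baseline through Visit 5.

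The cost is one changed number and one added sentence, by protocol amendment. No extra patients, procedures or analyses are needed. The same amendment is a convenient place to check the Visit 4 and 4-week wording in Sections 7, 8.2.2 and 8.3.

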6.2.1 Prohibited Concomitant Medications

Any stimulant (e.g., methylphenidate, dexmethylphenidate, amphetamine, and dextroamphetamine) should be discontinued 7 days prior to Baseline. The following medications are prohibited during the study:

Selective serotonin reuptake inhibitors (SSRIs) (e.g., paroxetine)

Serotonin and norepinephrine reuptake inhibitors (SNRIs) (e.g., desvenlafaxine, duloxetine, venlafaxine – with the exception of fluoxetine which is restricted for 30 days prior to Baseline) MAOIs

Mood stabilizers (e.g., lithium, valproate, quetiapine)

Antipsychotics (e.g., risperidone, olanzapine)

Anticonvulsants (e.g., phenobarbital, phenytoin, primidone)

Sedative hypnotics, except melatonin

Anticoagulants

Halogenated anesthetics

Tricyclic antidepressants

Atomoxetine

Guanfacine

Clonidine

CYP2D6 inhibitors (e.g., paroxetine and fluoxetine, quinidine, ritonavir)

Fentanyl, tramadol, tryptophan, buspirone, St. John's Wort

Gastrointestinal acidifying agents (e.g., guanethidine, reserpine, glutamic acid HCl, ascorbic acid)

Urinary acidifying agents (e.g., ammonium chloride, sodium acid phosphate, methenamine salts

Decongestants (e.g. oxymetazoline, phenylephrine, pseudoephedrine)

Sedating antihistamines (e.g. alimemazine, chlorphenamine, clemastine, cyproheptadine, hydroxyzine, promethazine)

Acetaminophen is permitted for control of fever or pain if needed. Short courses of prescription and non-prescription medications needed for treatment of acute illnesses such as the common cold, viral illnesses, and ear infections are permitted as long as these do not contain medications listed above. Ongoing antihypertensive treatment will be assessed by the Investigator and the Sponsor.

Confidential Page 38 of 67

Alcohol consumption will be restricted form Baseline to 24 hours after Visit 5.

All concomitant medications must be recorded on the Concomitant Medication CRF.

The Investigator should contact the Medical Monitor for a written Note to File or Memo to File for evidence that the Sponsor is aware of a chronic or acute medication and a judgment on whether the subject may continue in the study.

6.3 Treatment Compliance

Subject training at Baseline and subsequent ongoing retraining regarding proper dosing of study drug will occur to ensure subject compliance. Subjects must be instructed to return to every visit any unused study drug and/or the empty bottle. Starting with Visit 1, study staff will assess compliance by inspecting returned study drug bottles at every study visit to confirm that the subject is taking study drug according to the protocol. Drug accountability per subject will be recorded on drug accountability logs. If the subject forgets to bring the bottle to the visit, the visual inspection will occur when the bottle is returned.

6.3.1 Acceptable Compliance

Acceptable compliance is defined as 80% or higher which is inclusive.

If compliance between subsequent scheduled visits is outside this acceptable range and/or cannot be determined (when, for example, the subject did not return unused study drug), the Investigator or designee will determine subject's continued participation, after consultation with the Clinical Monitor and the Sponsor.

Confidential Page 39 of 67

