3.6 Subject Withdrawal Criteria

Within the provisions of informed consent and good clinical judgment with respect to the subject's safety, every attempt should be made to have subjects complete the study. The following are possible reasons to terminate the participation of any subject from the study:

Confidential Page 25 of 67

- Signs and symptoms of intolerance to the study medication.
- A treatment-related, serious adverse event (SAE) is observed.
- The subject is grossly non-compliant, as determined by the Investigator.
- Continued participation, in the opinion of the Investigator, is no longer in the best interest of the subject.
- The subject wishes to withdraw for any reason.
- Unblinding of the Investigator, site personnel performing assessments, or subject to a subject's treatment assignment.

Subjects will be encouraged to adhere to the protocol and complete all required assessments for the study. A subject may also be discontinued from the study for any of the following medical and/or administrative reasons:

- Pregnancy
- At the discretion of the Investigator at any time
- At the subject's request
- Occurrence of a Treatment Emergent Adverse Event (TEAE) or considerable worsening of an AE that represents an unacceptable risk to the subject and when continued participation in the investigational study is not warranted, in the judgment of the Investigator or the Sponsor. The Investigator must follow the subject until the AE resolves or satisfactorily stabilizes.

Any enrolled subjects desiring to discontinue prior to study completion should be encouraged to continue in the study and adhere to the protocol and subsequent regularly scheduled safety and effectiveness evaluations. Subjects who are discontinued outside of any scheduled visit will be encouraged to complete the final study visit at the time of withdrawal. Subjects who are discontinued during a scheduled visit will be encouraged to complete all assessments for both that study visit and the final study visit at the time of withdrawal. A subject who withdraws following study drug administration will not be replaced in their cohort.

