5.4 Drug Administration

The study drug will be administered orally once daily before 10 am with or without food. Subjects will be instructed to take each study drug dose by swallowing or chewing. Drug administration for Visits 4 and 5 will occur on-site.

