5.5 Investigational Drug Accountability

The Investigator or designee will verify and acknowledge receipt of the study drug. All study drug samples must be stored in a secure area under the proper storage requirements with limited access (i.e., restricted to the Investigator or designees). Medication designated for this clinical study must not be taken by any subjects other than those enrolled in this specific investigation and may not be utilized for any laboratory or animal research. All study drug dispensed to subjects must be accurately recorded on the Drug Accountability Record maintained at the study site. Subjects should be instructed to return all study drug dispensed to them (including remaining tablets and empty containers) at each study visit.

Drug accountability will be performed at each study visit starting with Baseline. Subjects will be provided with a new bottle containing 10 tablets at each visit (Baseline and Visits 1 to 4). Containers including the remaining study drug samples should be returned to the site at each subsequent visit. Remaining drug product samples and empty containers will be retained at the site for Study Monitor and/or Sponsor verification. All drug product samples should be stored at the study site until further instruction from the Sponsor.

Confidential Page 36 of 67

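### The compliance rule in section 6.3.1 has a floor of 80% but no ceiling, so on a tablet count countable over-use does not by itself start the consultation

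*Combined protocol and SAP*

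**What the plan says.** Section 6.3.1 of the protocol states: "Acceptable compliance is defined as 80% or higher which is inclusive". The next sentence says when that rule leads to action: "If compliance between subsequent scheduled visits is outside this acceptable range and/or cannot be determined". The example given for the second limb is "when, for example, the subject did not return unused study drug". In either case the Investigator or designee decides whether the subject stays in the study, after consulting the Clinical Monitor and the Sponsor.

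Section 6.3 says how compliance is judged. From Visit 1, staff do so by "inspecting returned study drug bottles at every study visit to confirm that the subject is taking study drug according to the protocol". No formula is given in 6.3, in 6.3.1 or elsewhere in the document. Section 9 refers to a detailed statistical analysis plan to be finalised before unblinding, but the text under review does not contain one.

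On supply, section 5.5 gives each subject a new 10-tablet bottle at Baseline and at each of Visits 1 to 4, against once-daily dosing and weekly visits with a window of 3 days either way (9.3.8). Section 5.4 adds: "Drug administration for Visits 4 and 5 will occur on-site".

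Other sections bear on over-use. Section 3.6 allows withdrawal on this ground: "The subject is grossly non-compliant, as determined by the Investigator". Section 5.6 says the Sponsor or its delegate "will review inventory forms during the study and at the conclusion of the study". Sections 8.7.2, 10.3 and 12.7 cover overdose, source verification and protocol deviations.

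**The concern.** The rule has a floor and no ceiling. The wording refers to a range and says the limit is inclusive, which would fit a two-sided rule, but no upper figure appears. That this was an omission is inference only.

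The study drug is amphetamine, and each weekly bottle holds more tablets than a nominal week needs. Compliance can therefore fail in two directions: too few tablets taken, or too many. A floor alone flags only the first. If the score is a tablet count, every count above 100% satisfies the rule, and the one numeric trigger that brings in the Clinical Monitor and Sponsor stays silent. At stake are subject safety and drug accountability, not the efficacy inference.

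**Working it through.** The 80% threshold is a definition, so there is no calculation of the plan's own to reproduce. The check is to apply the rule to possible bottle counts.

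**Inputs.** Threshold: at least 80% (6.3.1). Bottle: 10 tablets (5.5). Dosing: once daily (5.4). Nominal interval: 7 days (9.3.8).

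**Formula A (assumed, not written):** compliance = tablets not returned / scheduled take-home doses. The text favours this reading. Compliance is assessed from returned bottles, and the example of an undeterminable score is a failure to return drug. A bottle count does not show on which days tablets were taken.

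| Tablets gone | 7 scheduled doses | Current rule | 80% to 120% range |
|---|---|---|---|
| 5 | 5/7 = 71% | outside | outside |
| 6 | 6/7 = 86% | acceptable | acceptable |
| 7 | 7/7 = 100% | acceptable | acceptable |
| 8 | 8/7 = 114% | acceptable | acceptable |
| 9 | 9/7 = 129% | acceptable | outside |
| 10 | 10/7 = 143% | acceptable | outside |

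The bottles given at Visits 3 and 4 cover 6 nominal take-home doses if the on-site doses come from clinic stock, which is not stated. The scores are then 5/6 = 83%, 7/6 = 117%, 8/6 = 133% and 10/6 = 167%. All pass the current rule; 133% and 167% would fall outside 80% to 120%.

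The cleanest case is 9 tablets gone and 1 returned after 7 doses. The bottle came back with a countable remainder, the score is 129%, and the rule classes it as acceptable. If all 9 were swallowed at the 20 mg step, average intake would be 9 × 20 / 7 = 25.7 mg a day.

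**Formula B (the alternative):** compliance = days dosed as directed / days in the interval. Nine tablets could be two double-dose days and five single ones (2 × 2 + 5 × 1 = 9). That gives 5/7 = 71%, which is below the floor and starts the consultation. The same behaviour is classed in opposite ways under the two formulas, so the conclusion depends on A.

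**Short and long intervals under A.** At 10 take-home doses an emptied bottle is 10/10 = 100% and correct. At 5 doses one extra tablet is 6/5 = 120%, just inside the proposed range. At 4 it is 5/4 = 125%, which is why a tolerance is needed there.

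**What no interval percentage can show.** One double-dose day offset by one missed day uses 2 + 0 + 5 = 7 tablets, and 7/7 = 100%. One double-dose day with no missed day gives 8/7 = 114%, inside both the current rule and the proposed range.

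**The case against.** A reader might infer that over-use goes unnoticed, or that its escalation rests on site judgment alone. The documents do not support that. Section 12.7 requires all protocol deviations to be documented and reported to the Sponsor, and taking two tablets in a day departs from once-daily dosing. Inventory forms are reviewed during and after the study (5.6). Remaining drug and containers are held for verification (5.5). Monitors verify all source documents (10.3). An overdose without an adverse event is still recorded in the CRF (8.7.2). None of these depends on the 80% figure. They do not set an upper compliance limit or start the 6.3.1 consultation, but they narrow the gap to that one trigger.

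A reader might also take the fully emptied bottle (143%) as the plainest example. It is not. Three tablets beyond the scheduled 7 could have been swallowed, lost or kept, and a site could treat the last two as unused drug not returned, so that compliance is undeterminable and the consultation starts. Section 6.3 does accept an empty bottle as a return, so the point is arguable either way. With 9 gone and 1 returned, a site could reason similarly about the two missing tablets, but nothing requires it to, because a score exists and passes.

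The objection that the formula is unwritten stands, and the conclusion is conditional on it. So does the remark that exposure is bounded: bottles hold 10 tablets, the three spare tablets match the 3-day window for a late visit, and blood pressure, pulse and adverse events are checked at every visit. The 120% figure has no source in the documents beyond mirroring the floor.

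Finally, the wording of 8.7.2 on doses below 20 mg might be read as a second gap. That rests on one reading of a separate section and carries no weight here.

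**Conclusion.** The point holds in a limited form. The compliance trigger in 6.3.1 has no upper limit. If compliance is tablets not returned over scheduled take-home doses, countable over-use of 114% to 143% in a 7-dose interval is classed as acceptable and does not by itself start the consultation. This rests on formula A, which the bottle-inspection text favours but the protocol does not state.

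Severity is minor. It concerns safety oversight and accountability through one trigger, with several other routes to the Sponsor still open. It might be inferred that the efficacy results are also affected. They are not: compliance defines none of the analysis populations in 9.2, safety data are summarised by treatment group (9.3.6), and no efficacy, power or alpha figure depends on it.

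**What to change.** In 6.3.1, replace the one-sided limit with a two-sided range and name the ratio it applies to. For example: 80% to 120% inclusive of tablets not returned divided by scheduled take-home doses since dispensing, with one tablet above 100% tolerated when there are 4 or fewer such doses. Counts above the range would start the consultation already described there, and the decision on continued participation stays as written. The 120% is a proposal; another justified ceiling would serve. At 7 doses it treats both sides alike, accepting one missed or one extra tablet (86%, 114%) and flagging two (71%, 129%).

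The change is a sentence or two and uses counts already made at every visit. It belongs in the protocol, not in an analysis plan finalised before unblinding, because sites apply the rule visit by visit. The cost is a few extra queries about tablets that turn out to be lost. It does not detect a single double-dose day and should not be presented as doing so.
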